UCOPE Protocol

1. Project Title

Mechanisms of Oxytocin's Analgesia in Older Adults (Short title: UCOPE Study: **U**nderstanding **C**ognition, **O**xytocin, and **P**ain in **E**lders)

2. Investigator(s)

[name] (PI)
[name] (co-PI)
[name] (co-I)
[name] (co-I)
[name] (co-I)

3. Abstract

Osteoarthritis (OA) represents a significant cause of disability worldwide in individuals aged 65 and older, a rapidly growing segment of our population. The knee is the most commonly affected joint with pain being the primary symptom, negatively impacting physical, cognitive, and emotional functioning. Symptomatic knee OA has been traditionally attributed to peripheral mechanisms, but measures of joint damage only modestly account for the presence or severity of OA-related pain. The neuropeptide oxytocin (OT) has been recognized as a mediator of endogenous analgesia in animal and human studies. However, little is known about the neurobiological mechanisms underlying OT's pain-relieving properties. This proposal is based on a mechanistic model of OT's analgesic effects leveraging pilot data supporting efficacy and safety of self-administered intranasal OT over 4-weeks in older individuals. Relative to placebo (P), daily administration of intranasal OT diminished self-reported pain intensity, reduced experimental pain sensitivity, and increased self-reported physical and emotional functioning. Further, participants treated with OT, compared to P, showed decreases in brain metabolite concentrations associated with inflammation. Thus, our overarching goal is to evaluate the effects of intranasal OT on pain and function in aging and to determine the extent to which central and peripheral inflammatory mechanisms contribute to these analgesic responses. We aim to 1) determine the effect of intranasal OT administration on clinical and experimental pain sensitivity in older adults with symptomatic knee OA and 2) characterize inflammatory mechanisms contributing to the inter-individual variability in analgesic responses to OT. Older adults with symptomatic knee OA will self-administer intranasal OT or P over 4 weeks using a double-blinded, cross-over study design. With strong support from the University of Florida and the McKnight Brain Institute, our interdisciplinary project, using a comprehensive multi-methods approach, will be the first to determine the potential benefit of OT as a novel analgesic therapy for knee OA pain in aging. OT is currently used in obstetrics and may be an inexpensive, effective method for pain management in older adults with little potential for addiction. Embedded in a biopsychosocial framework, our proposal will help pave the way for future investigations using a mechanism-based treatment optimization strategy for individuals suffering from chronic pain.

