Specific Aim 2: To characterize inflammatory mechanisms contributing to the inter-individual variability in analgesic response to OT. We will assess central and peripheral inflammatory processes using proton MRS in frontal brain regions and plasma immune markers, respectively. Based on our preliminary data, we hypothesize that compared to P, OT administration will result in significant: **H2a**) decrease in plasma levels of IL-6, TNF- α , and IL-10; and **H2b**) decrease in brain metabolite concentrations associated with inflammation (i.e., *MI*, Cr, Cho). Further, **H2c**) decrease in brain metabolites and systemic cytokines will be significantly associated with decrease in clinical pain intensity. Other markers of brain structure and function will also be significantly associated with changes in clinical pain intensity (**H2d**).

Exploratory Aim 3: To characterize effects of acute intranasal OT administration on clinical and experimental pain as well as underlying neurobiological mechanisms in younger and older controls. We will perform similar experiments as above in control participants to further understand OT's analgesic effects across the lifespan in the absence of knee OA pain. However, acute OT administration will be used in healthy controls versus chronic administration in the presence of Knee OA.

6. Research Plan

We propose a double-blinded, randomized cross-over design that will randomize older adults with symptomatic knee OA pain and/or back pain to four weeks of intranasal self-administration of either OT or P (48 IUs daily) followed by a four-week washout period and a second four weeks of intervention (either OT or P). Our study design was guided by recommendations by the IMMPACT group for clinical pain trials.⁷⁴⁻⁷⁷ After initial screening, eligible participants will undergo up to four baseline sessions (health, sensory, and neuroimaging) for collection of clinical, functional (physical, cognitive, emotional), QST, and brain imaging data lasting 2-3 hours. At some point during the baseline, intervention, and post-intervention periods, participants may wear a Samsung Gear S[®] or Apple smartwatch or Oura ring to obtain daily pain, mood, and social activity assessments and to objectively measure physical activity levels and sleep quality. During the intervention, participants will self-administer twice daily 24 IUs

Protocol: IRB201801467 (UCOPE Study)

IRB version: 10/1/2018

PI version: 05/10/2024

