(e.g., for osmolality levels, sodium levels, and any other blood markers out of range) to ensure that no adverse changes have occurred during the study intervention. Additionally, before and after the intervention period participant will fill out the Goal Attainment Scale (**GAS**). For the majority of the 4-week intervention periods, participants may complete daily assessments via their Samsung Gear S® or Apple smartwatch or Oura Ring. We will be able to assess pain, mood, and activities at random times throughout the day. Participants will be contacted once a week to assess side effects and asked if they have been completing their diaries. Any symptom reported as moderate or severe will be brought to the PIs' attention and will be discussed with the study MD as needed on a case by case basis. These weekly calls will also ensure regimen compliance and will assist participants in download of the Samsung Gear S® or Apple smartwatch or Oura Ring data to a secure research server. We have successfully established a similar approach in other projects within our institute, and the DSAT Core has validated pipelines for data analysis.^{92,106}

Post-Intervention Assessments for Knee OA Participants

In the last week of the intervention, participants will be scheduled to return for up to four (or 6 with the MRI) post-intervention visits, which will be identical (with minor exceptions) to the baseline visits. Importantly, at the follow-up Health Assessment we will assess changes in health status, and their global impression of change (**PGIC/MPIC**) since starting the intervention.

Wash-out Period for Knee OA Participants

Participants will undergo a four-week wash-out period in between phases one and two. The wash-out period will serve to prevent confounding variables between both drug administrations. Four weeks is a sufficient period of time for participants to return to baseline levels prior to drug administration.

Phase Two Procedures for Knee OA Participants

After the four-week wash-out period, participants will enter phase two of the study. Phase Two is completely identical to Phase One: up to 4 (or 6 with the MRI) Baseline Visits, Intervention Period, and up to 4 (or 6 with the MRI) Post-Intervention Visits. Participants will be given the other drug from the first intervention period per randomization.

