We will compensate control participants with up to \$330 upon study completion in the form of a pre-paid, reloadable VISA card issued by the University of Florida or by cash payments. In particular, for completion of

- Screening Visit, Baseline Visit: \$75
- Sensory Visit: \$75
- Neuroimaging Visits (up to 2 visits): \$75 per visit
- (Optional) extra \$30 if you choose to participate in the nasal spray treatment.

Power and sample size considerations: Based on our pilot study estimates, we plan to recruit 160 participants, i.e., 80 participants in each of the randomly assigned treatment groups for the baseline visits. Assuming an attrition rate of 20% at the follow-up visits, we will have 128 participants (64 in the OT and 64 in the P group) at the 4-week post-intervention follow-up visits. This sample size yields a power over 0.80, even based on a very conservative Bonferroni correction for multiple comparisons (i.e., testing twelve hypotheses), which lowers the alpha level from $\alpha=0.05$ to $\alpha=0.006$. However, our proposed data-analytic strategy will use the Benjamini and Hochberg procedure to control for multiple comparisons, which is less stringent than the Bonferroni correction, and thus we expect the actual power to be larger than 0.80.

Hypotheses and data-analytic strategy: We summarize all hypotheses and planned analyses in **Table 3 for aims 1 and 2.** The statistical analyses will be conducted by Co-I [name] (Biostatistician) in

Protocol: IRB201801467 (UCOPE Study)

IRB version: 10/1/2018

PI version: 05/10/2024

collaboration with [name] (Consultant, Institute on Aging Biostatistics and Bioinformatics Core Leader, see letter of support) using R software. For studying the relationship between pre- to post-intervention (longitudinal) outcomes and predictors, we will fit linear mixed effects models (**LMEMs**) [1] with subject specific random effects to account for the within-subject correlation, by R function “lmer”.¹⁰⁹ Baseline outcomes and covariates will be adjusted to take account for confounding effects. Below is the formula for the linear mixed effect model:

$$y_{ik} = \mu + \alpha_i + \beta \mathbb{I}(z_i = 1) + \sum_{l=0}^L \gamma_l x_{il} + \eta \mathbb{I}(k = 2) + \theta \mathbb{I}(z_i = 1, k = 2) + \varepsilon_{ik}, \alpha_i \sim N(0, \sigma_0^2), \varepsilon_{ik} \sim N(0, \sigma^2) \quad [1]$$

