where y_{ik} is the outcome variable (e.g., pain intensity/sensitivity/function for Aim 1) for subject i and visit k ($k = 1$ for intervention and $k = 2$ for post-intervention); μ is the intercept term; $\alpha_i \sim N(0, \sigma_0^2)$ is the random effect with variance term σ_0^2 for subject i ; z_i is the treatment indicator with $z_i = 0$ for P and $z_i = 1$ for OT, β is the treatment effect (OT effect compared to P effect) and $\mathbb{I}(\cdot)$ is the indicator function which equals 1 if the argument inside (\cdot) is true and equals 0 otherwise; x_{il} is the l^{th} covariates for subject i with $l = 0$ for baseline level (e.g. baseline pain intensity before treatment for Aim 1) and $l = 1, 2, \dots, L$ for L covariates (i.e., age, sex, race...); η is the time effect of post-intervention visit compared to pre-intervention visit; θ is the interaction effect between post-intervention and OT; $\varepsilon_{ik} \sim N(0, \sigma^2)$ is the error term with variance σ^2 . From equation [1], we will test whether there is a significant OT effect for both intervention and post-intervention. LMEMs allow for missing data if missing-at-random (MAR).

Table 3. Proposed hypotheses and planned analyses.

Specific Aims	Hypotheses	Planned Analyses
#1: Clinical and experimental pain	H1a: OT vs. P administration will reduce self-reported pain intensity	LMEMs* ; DV: Clinical pain IV: Treatment (OT/P)
	H1b: OT vs. P administration will decrease experimental pain sensitivity	LMEMs* ; DV: QST IV: Treatment (OT/P)
	H1c-1e: OT vs. P administration will increase physical, cognitive and emotional function	LMEMs* ; DV: SPPB, Exe. Function, Catastrophizing IV: Treatment (OT/P)
#2: Inflammatory mechanisms	H2a: OT vs. P will decrease systemic inflammation	LMEMs* ; DV: Plasma cytokines (IL6, TNF α , IL10) IV: Treatment (OT/P)
	H2b: OT vs. P will decrease brain metabolite concentrations associated with neuroinflammation	LMEMs* ; DV: Brain metabolites (tCr, MI, Cho) IV: Treatment (OT/P)
	H2c: Decrease in brain metabolites and systemic cytokines will be associated with decrease in clinical pain	Correlations/ Regressions IV: Decrease in brain metabolites and systemic cytokines DV: Decrease in clinical pain

Note. **IV** = Independent variable; **DV** = Dependent variable; **LMEMs**: linear mixed effects models; *Adjusted for baseline outcomes and covariates (age, sex, race, BMI, KL score, hip OA, plasma biomarkers).

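### The trial is a two-period crossover, but equation [1] and the power statement describe a two-arm parallel trial, so the plan does not define a valid use of the second period

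*Combined protocol and SAP*

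**What the plan says.** The design is stated consistently as a crossover. The Abstract describes treatment over four weeks "using a double-blinded, cross-over study design". The opening of section 6 (Research Plan) has four weeks of OT or P "followed by a four-week washout period and a second four weeks of intervention (either OT or P"). Under Phase Two Procedures for Knee OA Participants, the second phase repeats the first, including new baseline visits, and "Participants will be given the other drug from the first intervention period per randomization".

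The statistical text describes something else. Under Power and sample size considerations: "we plan to recruit 160 participants, i.e., 80 participants in each of the randomly assigned treatment groups for the baseline visits". After allowing for a 20% loss, the same paragraph concludes: "we will have 128 participants (64 in the OT and 64 in the P group) at the 4-week post-intervention follow-up visits".

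Equation [1], under Hypotheses and data-analytic strategy, is a linear mixed model for subject i at visit k. Treatment enters as z_i (0 for P, 1 for OT), with a subject index only. Its coefficient beta "is the treatment effect (OT effect compared to P effect"). There are two visits, one baseline covariate per subject, a visit effect, a treatment-by-visit interaction and a random subject intercept. There is no period index, period effect or sequence term. Table 3 and the text after it apply this model to H1a to H1e (which include the primary pain outcome), H2a and H2b. No crossover analysis appears elsewhere in the UCOPE text. Carryover is mentioned only for the order of the sensory tests.

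**The concern.** In this crossover no completer has a single value of z_i, because each has been on both drugs. The written model therefore leaves open how second-phase records enter the primary test. There are two ways to apply it literally:

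- **Use Phase One only.** This is a valid randomised comparison, but the second phase contributes nothing to the primary test.
- **Enter both phases under the first-assigned drug.** Every second-phase record then carries the wrong treatment label.

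An analyst could also fit a proper within-subject model, but the plan does not specify one. These analyses differ about twofold in standard error, and one of them estimates nothing, so the choice should not be open once data are seen. If both phases are used without a period term, practice or time trends in sensory testing, cognition and pain go into the error. They also go into the treatment estimate if dropout differs by sequence.

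**Working it through.** **Inputs from the plan.** 160 recruited; 20% attrition; 12 hypotheses; a stated corrected alpha of 0.006; power above 0.80. The plan gives no effect size, SD, within-subject correlation or sidedness. Two-sided tests and the correlations rho below are assumptions.

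**The plan's own figures.** Attrition reproduces: 160 × 0.80 = 128, or 64 + 64. The alpha does not: 0.05/12 = 0.0042, while 0.05/8 = 0.00625 and 0.05/9 = 0.0056 round to 0.006. That is a separate point. The power cannot be reproduced without an effect size. It can only be inverted: with 64 v 64 and no baseline adjustment, the detectable effect is d = (z for 1 − alpha/2 + z for 0.80) × √(2/64). This gives 0.63 SD at alpha 0.006 and 0.66 SD at alpha 0.05/12.

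**Counting observations.** If 128 people complete both phases, there are 128 outcomes on OT and 128 on P, not 64 and 64.

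**Precision.** Take outcome SD 1, and let rho be both the correlation between a subject's two period outcomes and that between baseline and outcome.

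- Phase One only, baseline-adjusted: variance = 2(1 − rho²)/64
- Within-subject contrast, 128 completers: variance = 2(1 − rho)/128
- Ratio = 2(1 − rho²)/(1 − rho) = 2(1 + rho)

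| rho | Variance ratio | Detectable, Phase One only (alpha 0.05/12) | Detectable, crossover (alpha 0.05/12) | Same pair at alpha 0.006 |
|---|---|---|---|---|
| 0.3 | 2.6 | 0.63 SD | 0.39 SD | 0.605 v 0.375 |
| 0.5 | 3.0 | 0.57 SD | 0.33 SD | 0.550 v 0.317 |
| 0.7 | 3.4 | 0.47 SD | 0.25 SD | 0.453 v 0.246 |

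**Stacking both phases under one z_i.** Let tau be the OT effect and p1, p2 the period means, with no carryover. Averaged over the two phases, the OT-first group has mean (p1 + tau + p2)/2 and the P-first group (p1 + p2 + tau)/2. The difference is zero whatever tau is. Simulation agrees: 4,000 trials with 64 per sequence and rho 0.5 gave a mean estimate of 0.00 when the true effect was −0.50 SD, and again when it was −0.60 SD. In the −0.60 runs, Phase One alone without baseline adjustment gave −0.60 (SE 0.177) and the within-subject contrast −0.60 (SE 0.088). The squared ratio of these SEs is about 4.0. The 3.0 in the table is lower because that comparison is baseline-adjusted: √(2 × 0.75/64) = 0.153 against √(2 × 0.5/128) = 0.088.

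**Could k stand for period?** The plan defines k as the intervention and post-intervention visits, so no. If it were read as period with z_i the first drug, the Phase One contrast would be beta = tau and the Phase Two contrast beta + theta = −tau. The OT effect would then be reported with opposite signs in the two phases.

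**The case against.** The strongest reply has three parts.

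- **The cancellation is hypothetical.** The plan nowhere says that second-phase records keep the first-phase label. Table 3 names the predictor only as treatment, OT or P, and a competent statistician would code the drug actually taken. This stands as a limit: the zero estimate depends on stacking under a fixed z_i. It does not remove the problem, because the printed formula has no index by which treatment could change within a subject, and a random intercept cannot correct a label that never changes.
- **Phase One alone gives an unbiased answer, free of carryover.** True. The cost there is precision and unused data. If this was the intention, the plan must say so, because Phase Two would then have no part in the primary test.
- **The power mismatch is conservative.** Also true. If 64 v 64 gives power above 0.80 for some effect, a crossover analysis of 128 completers gives more.

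The size of the gain is less certain than its direction. The plan places attrition at the four-week follow-up and does not address loss across the washout and second phase. If a further 20% left (an assumption), about 128 × 0.8 = 102 would complete both, and the crossover detectable effect at rho 0.5 and alpha 0.05/12 would rise from 0.33 to 0.37 SD. The MRI is optional, so 128 need not apply to H2b.

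**Conclusion.** The concern holds. The primary model and the power basis do not describe the trial being run, and the role of the second period in the primary test is undefined. Using one period only costs a variance factor of 2.6 to 3.4 for rho from 0.3 to 0.7. Stacking both periods under the first-assigned drug removes the OT effect altogether. The first figure assumes 128 completers of both periods, equal variances and one rho for both correlations. The second assumes no carryover and balanced retention. Neither shows that the sample is too small. The point should be settled before analysis because it concerns the specification of the primary test.

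**What to change.** Replace equation [1] with a crossover mixed model on the end-of-period outcomes:

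y_ip = mu + period_p + tau × OT_ip + baseline terms + covariates + random subject intercept + error,

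where OT_ip marks the drug subject i received in period p, and the baseline terms are the period baseline and the subject's mean baseline. Other baseline parameterisations are acceptable if stated in advance. Test tau.

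In the same revision:

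- Drop or redefine the visit index k. Assessments fall at baseline and in the last week of each period, and the text calls the reference visit intervention in one place and pre-intervention in another.
- Say how participants with only one period are handled, and keep a Phase One-only comparison as a sensitivity analysis for carryover.
- Restate power on the within-subject contrast, giving the effect size, SD, within-subject correlation, sidedness and expected number completing both periods. Describe the 80 + 80 as sequence groups.

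If a first-period primary analysis is what was meant, say so and give the purpose of Phase Two.

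The cost is rewording of the analysis and power sections. No new data, visits or participants are needed.

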For **Aim 1**, the primary outcome will be self-reported pain, and plasma levels of OT as a modifier of a significant treatment (OT vs. P) response, using an intent-to-treat approach. Secondary outcomes include a standardized, multimodal experimental pain battery and physical, cognitive, and emotional functioning measures. For hypotheses **H1a** to **H1e**, we will use equation [1] to evaluate and test the effect of OT at 4-weeks post-intervention compared to P. Baseline outcomes and covariates (age, sex, race, hip OA, and inflammatory biomarkers) will be properly adjusted. A 50% reduction in self-reported pain intensity will demonstrate a clinically significant effect of OT compared to P. For **Aim 2**, the primary outcomes are proton MRS metabolites in frontal brain regions (tCr, MI, Cho) and plasma immune markers (IL-6, TNF- α , IL-10). For hypotheses **H2a** and **H2b**, we will use equation (1) to evaluate changes from baseline to post-intervention. Covariates (age, sex, race, hip OA) will be properly adjusted. For hypothesis **H2c**, we will use correlational tests and regression methods to evaluate the association between brain metabolites, systemic cytokines, and clinical pain to consider the inter-individual variability in treatment response. Consistent with IMMPACT recommendations we will perform a secondary analysis considering total number and amount of rescue medication doses in a matrix alongside pain relief, with higher scores assigned to those patients with high levels of relief and minimum rescue, and lower scores assigned to patients who have rescued the most and have lower pain relief scores.⁷⁷ For exploratory aim 3, similar strategies will be employed.

7. Possible Discomforts and Risks

Equipment used in this research meet all current safety standards, and all research staff will be highly trained in the use of all equipment. This study may include risks that are unknown at this time. Potential risks for this study are related to use of study product, neuroimaging, blood draw procedure, blood pressure measurement, the physical performance tests, the cognitive function tests, the sensory testing, and potential loss of confidentiality related to study participation, as discussed in detail below.

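### The Bonferroni alpha of 0.006 in the power statement does not match the twelve hypotheses named beside it: 0.05/12 is 0.0042

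*Combined protocol and SAP*

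**What the plan says.** Section 6 (Power and sample size considerations) plans 160 participants, 80 per group, and expects 128 (64 per group) after 20% attrition. It says that power then exceeds 0.80, "even based on a very conservative Bonferroni correction for multiple comparisons (i.e., testing twelve hypotheses), which lowers the alpha level from" 0.05 to 0.006. The next sentence says that the analysis itself will use the Benjamini-Hochberg procedure. Because that is less strict than Bonferroni, the authors expect the actual power to be higher still.

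The family of tests is not listed in that paragraph. Three other places bear on it:

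- The data-analytic strategy opens with "We summarize all hypotheses and planned analyses in" Table 3, for Aims 1 and 2. Table 3 labels eight hypotheses: H1a to H1e and H2a to H2c.
- Some rows of Table 3 carry several outcomes. H1c-1e has "DV: SPPB, Exe. Function, Catastrophizing IV: Treatment (OT/P"), H2a has three cytokines, and H2b has "DV: Brain metabolites (tCr, MI, Cho) IV: Treatment (OT/P"). The text on Aim 2 likewise says that "the primary outcomes are proton MRS metabolites in frontal brain regions (tCr, MI, Cho) and plasma immune markers", and then names three of the latter.
- Section 5 adds H2d, which is not in Table 3: "Other markers of brain structure and function will also be significantly associated with changes in clinical pain intensity".

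**The concern.** A Bonferroni alpha is the overall level divided by the number of tests, so the sentence can be checked from its own figures. Twelve tests at 0.05 do not give 0.006. This is the only per-test alpha given for the power claim, and no effect size or SD accompanies it, so a reader cannot tell whether the claim survives at the alpha that belongs to twelve tests.

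The step to Benjamini-Hochberg is affected too. For the same family and level, Benjamini-Hochberg rejects everything that Bonferroni rejects, so Bonferroni power is a valid floor. If the family has twelve tests, that floor is the power at 0.0042. Power at 0.006 is a looser figure, and the argument from it does not go through as written.

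**Working it through.** **Inputs from section 6:** overall alpha 0.05, stated count 12, stated alpha 0.006, 64 per group. Sidedness, effect size and SD are not given.

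**The plan's own figure.** 0.05/12 = 0.00417, which rounds to 0.004. The stated 0.006 is not reproduced. The usual variants at twelve tests do not give it either: Šidák 1 − 0.95^(1/12) = 0.00427; one-sided 0.025/12 = 0.00208; overall level 0.10, 0.10/12 = 0.00833. Twelve tests at 0.006 sum to 12 × 0.006 = 0.072, above 0.05.

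**Which counts fit 0.006.** An alpha rounds to 0.006 if it lies between 0.0055 and 0.0065. So the count m lies between 0.05/0.0065 = 7.69 and 0.05/0.0055 = 9.09, which means m = 8 (0.00625) or m = 9 (0.0056). The neighbours fail: m = 7 gives 0.0071 and m = 10 gives 0.0050.

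**Which counts the documents offer.**

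- Eight: the labelled hypotheses in Table 3.
- Nine: those eight plus H2d from section 5.
- Twelve: the dependent-variable entries in Table 3. H1a 1 + H1b 1 + H1c-1e 3 + H2a 3 + H2b 3 + H2c 1 = 12.

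So 0.006 fits the first two counts, and the word twelve fits the third.

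**Size, as an illustration.** I assumed two-sided t-tests and used the noncentral t distribution. The planned model is a baseline-adjusted mixed model, so these figures show scale only. The parallel case follows the plan's 64 per group: 126 degrees of freedom, noncentrality d × √(64/2). Because the trial is described as a cross-over, I also took a paired test on 128 completers: noncentrality d × √128 / √(2(1 − ρ)), with the within-person correlation ρ assumed to be 0 or 0.5.

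| Alpha | Power, if exactly 0.80 at 0.006 | Detectable d, parallel | Paired, ρ = 0 | Paired, ρ = 0.5 |
|---|---|---|---|---|
| 0.00625 (8 tests) | 0.804 | 0.642 | 0.454 | 0.321 |
| 0.006 (stated) | 0.800 | 0.644 | 0.456 | 0.322 |
| 0.0056 (9 tests) | 0.793 | 0.649 | 0.459 | 0.324 |
| 0.0042 (12 tests) | 0.764 | 0.666 | 0.471 | 0.333 |

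Detectable d is at 0.80 power. The power column is the same on both bases. The detectable effect at 0.0042 relative to 0.006 is 0.6662/0.6442 = 1.034, and the paired cases give the same ratio. A normal approximation for the parallel case gives 0.766 in place of 0.764.

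**When the claim survives at twelve.** Power at 0.0042 reaches 0.80 if power at 0.006 was at least 0.8325, which in the parallel case means d of at least about 0.666.

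**The case against.** The best reply is that the figure matters little. The plan attributes the 160 to pilot estimates, uses Bonferroni only as a worst-case remark, and will analyse with Benjamini-Hochberg, so no planned test will use 0.006. That stands, and it limits the point to the wording of the power statement. It does not make the figure right: the remark is offered as the conservative case, and for twelve tests it is not.

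A second reply is that the count of twelve is a reconstruction. It counts clinical pain under both H1a and H2c, treats the sensory battery as one outcome, and treats H2c as one test although it has several predictors. Distinct outcomes number eleven. Nine is also open to doubt, because H2d has no row in Table 3 and no analysis assigned to it. This stands as well: the documents do not say how the family was formed, and each count is only a possible reading. But that supports the conclusion that the family is undefined. No reading makes twelve and 0.006 agree.

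A third reply is that the t-test figures go beyond what the documents allow, since the correlations are assumed and the planned model is different. They are given for scale only.

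**Conclusion.** The inconsistency is certain and rests on division alone: twelve tests give 0.0042, and 0.006 needs eight or nine. Which number is the slip cannot be settled from the documents.

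The consequence is minor. On the two-sided t-test assumptions above, a design with exactly 0.80 power at 0.006 would have 0.764 at twelve tests, a loss of 3.6 points, or 0.793 at nine. If eight is meant, the power is marginally higher than claimed. Because no effect size is given, the actual power is unknown and a shortfall is not shown. Type I error control under Benjamini-Hochberg, the planned models and enrolment are not affected.

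**What to change.** In the power paragraph, list the tests that form the family and make the two numbers agree: eight with 0.00625, nine with 0.0056, or twelve with 0.0042. If H2d is counted, add it to Table 3. Then restate the power, or the detectable effect, at that alpha, and give the pilot effect size and SD it was computed from so that it can be checked.

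The cost is a short list, one corrected figure and a rewritten sentence. The only downside is that the power may read slightly lower if twelve stands. The Benjamini-Hochberg sentence, the analysis and the sample size can stay as they are.

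### Self-reported pain is the Aim 1 primary outcome but appears to sit in one Benjamini-Hochberg family of twelve, so its threshold depends on the other outcomes, and power above 0.80 is not assured

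*Combined protocol and SAP*

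**What the plan says.** Under Hypotheses and data-analytic strategy (section 6), the plan states that for Aim 1 "the primary outcome will be self-reported pain". Experimental pain and physical, cognitive and emotional function are secondary. For Aim 2, three brain metabolites and three plasma immune markers are called primary.

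Power and sample size considerations, in the same section, expects that "we will have 128 participants (64 in the OT and 64 in the P group) at the 4-week post-intervention follow-up visits" and continues: "This sample size yields a power over 0.80". It says that this holds even under a "very conservative Bonferroni correction for multiple comparisons (i.e., testing twelve hypotheses"), which it equates with an alpha of 0.006. It then says that "our proposed data-analytic strategy will use the Benjamini and Hochberg procedure to control for multiple comparisons, which is less stringent than the Bonferroni correction", and concludes: "thus we expect the actual power to be larger than 0.80".

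The plan does not list the members of the Benjamini-Hochberg family, give the false discovery rate q, set a testing order, or exempt H1a. It gives no effect size or standard deviation for the power figure, only a reference to pilot estimates.

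**The concern.** Naming one primary outcome normally means that it is tested on its own terms. Here the label has no stated effect on how pain is tested. If H1a is one of twelve hypotheses under Benjamini-Hochberg, the p-value it must reach is not fixed in advance. It depends on how many cognitive, functional, cytokine and metabolite tests also come out small. The same pain data could then support opposite conclusions on the trial's main clinical question.

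The power sentence adds a second difficulty. It argues from a less stringent procedure to a power above 0.80, but its starting alpha does not match its own number of hypotheses. The reader cannot tell what power H1a has under the rule that will be applied.

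**Working it through.** **Inputs.** From the power paragraph: overall alpha 0.05; stated adjusted alpha 0.006; twelve hypotheses; 64 per group. Assumed, because not stated: two-sided tests, q = 0.05, and the normal approximation for two parallel groups, which is how that paragraph counts participants.

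**1. The stated alpha.** Bonferroni alpha = 0.05/m.
- m = 12: 0.05/12 = 0.00417, not 0.006.
- m = 8: 0.00625. m = 9: 0.00556. Both round to 0.006.

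Table 3 carries eight labels (H1a to H1e, H2a to H2c); the Specific Aims add H2d, making nine. The power figure itself cannot be reproduced without an effect size.

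**2. The family.** H1a to H1e (5) + three cytokines (3) + three metabolites (3) + H2c (1) = 12. This matches the stated count but is a reconstruction.

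**3. The threshold for pain.** Benjamini-Hochberg finds the largest R for which the R-th smallest p-value is at most R × q/m, and rejects every hypothesis with p at or below R × q/m. With m = 12:
- R = 1: 0.05/12 = 0.0042.
- R = 12: 0.05.

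Take p = 0.02 for pain. If every other p-value exceeds 0.05, pain is not significant, because 0.02 > 0.0042. If four others are at or below 5 × 0.05/12 = 0.0208, then R is at least 5 and pain is significant. This step needs no effect size and no assumption about the design layout.

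**4. Power if it is exactly 0.80 at 0.006.**
- Noncentrality = 2.748 + 0.842 = 3.589, which at 64 per group is d = 3.589 × √(2/64) = 0.635.
- Bonferroni at 0.05/12: Φ(3.589 − 2.865) = 0.766.
- Alone at 0.05: Φ(3.589 − 1.960) = 0.948.

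**5. Power for pain under 12-test Benjamini-Hochberg at the same effect.** Simulation with 300,000 replicates; correlation between outcomes 0 to 0.6; other true effects of the same size as pain.

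| Other true effects | Power for pain |
|---|---|
| None | 0.769 to 0.772 |
| Five | 0.894 to 0.907 |
| All eleven | 0.933 to 0.946 |

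**6. Where the 0.77 comes from.** If power is set to 0.80 at the matching level 0.05/12 (d = 0.655), 12-test Benjamini-Hochberg gives 0.804 to 0.806 with pain as the only effect. If there are eight tests and d = 0.635, it gives 0.808 to 0.810. When alpha and count agree, power stays just above 0.80, so the shortfall comes from pairing twelve tests with 0.006.

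**7. When the shortfall disappears.** With pain the only effect, power of 0.82 at 0.006 gives about 0.79 under 12-test Benjamini-Hochberg, and 0.83 at 0.006 (d = 0.654) gives 0.804.

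**8. False positives for pain under 12-test Benjamini-Hochberg.** If pain has no effect, it is declared significant with probability 0.005 when all twelve are null, and 0.050 when the other eleven are strongly positive.

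**The case against.** The strongest reply has four parts.

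- **The single family is not written down.** The count of twelve explains a hypothetical Bonferroni bound, and the Benjamini-Hochberg sentence names no members. This stands, so the pooled family is described here as apparent. It does not remove the problem: with the eight labels of Table 3, H1a is still a member, and its threshold would run from 0.00625 to 0.05.
- **Benjamini-Hochberg does not cost power against Bonferroni.** At the same number of tests it rejects everything that Bonferroni rejects. A reader might infer from 0.77 that the choice of Benjamini-Hochberg makes the power claim fail. The documents do not support that: the cause is the mismatch in steps 1 and 6, and without an effect size a shortfall is possible but not shown. It also stands that the gain over Bonferroni may be negligible, about 0.005 when pain is the only effect.
- **The other outcomes are not unrelated, and pooling does buy error control.** A reader might infer the opposite on both counts. The companions are experimental pain, function and the inflammatory markers thought to drive the analgesia, and six of them are labelled primary for Aim 2. Step 8 shows that pooling is at least as strict on H1a as a test at 0.05. But one pre-specified primary test at 0.05 already has its error rate controlled and does not need that extra strictness.
- **Testing H1a alone assumes that H1a is one test.** This stands. Clinical pain is assessed by both the verbal descriptor scale and WOMAC, Table 3 says only clinical pain, and the text after equation [1] tests the oxytocin effect at both visits. The fix must settle this too.

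**Conclusion.** The concern holds in a limited form. No text protects the Aim 1 primary outcome from the multiplicity adjustment. On the natural reading its threshold varies twelvefold, from 0.0042 to 0.05, with the other results. That rests on two assumptions: a single family of twelve and q = 0.05.

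Power above 0.80 for H1a is not assured, but it is not shown to fail. At the reference effect, pooled power runs from about 0.77 (pain the only effect) to about 0.95 (all twelve real and independent), against 0.948 if H1a is tested alone. The 0.77 applies only if there are twelve tests and power at 0.006 is exactly 0.80.

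The values of d follow the plan's count of two parallel groups, although the design is a cross-over. With 128 paired completers and an assumed within-person correlation of 0 to 0.7, 80% power at 0.006 needs d of about 0.45 to 0.25, so the true power may differ. The dependence of the pain threshold on the other outcomes does not change with the layout.

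**What to change.** Before unblinding, amend section 6 as follows:

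- Name one pain measure and one treatment contrast as H1a, and test it alone at two-sided 0.05.
- Apply Benjamini-Hochberg separately to the Aim 1 secondary hypotheses and to the Aim 2 hypotheses. List the members of each family and state q.
- Correct 0.006 to 0.0042, or correct the count of twelve.
- Replace the sentence that infers power above 0.80 from Benjamini-Hochberg with the power for H1a at 0.05, giving the effect size and standard deviation used.

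On the plan's own count of 64 per group, testing H1a alone lowers the smallest effect detectable with 80% power from d = 0.635 (alpha 0.006) or 0.655 (alpha 0.05/12) to (1.960 + 0.842) × √(2/64) = 0.495.

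The cost is wording only, with two statistical consequences. The false discovery rate is controlled within each family and not across all twelve tests, and H1a loses the stricter-than-0.05 threshold that pooling would sometimes impose.
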